#### **4.1.2.7. Overall survival (OS)**

Overall survival (OS): It is defined as the time from the date of first administration to death due to any cause.

Censoring rules are as follows:

- If the subject withdraws and is still alive, the censoring date is the last follow-up date when the survival status is obtained.
- If the subject is lost to follow up, the censoring date is the last follow-up date when the survival status is obtained prior to the lost of follow-up.

#### **4.1.2.8. 6/9/12/15/18-month overall survival (6/9/12/15/18-month OS%)**

It is defined as the 6/9/12/15/18-month overall survival (OS) after the date of first administration. The 6/9/12/15/18-month OS will be estimated by Kaplan-Meier method.

#### **4.1.2.9. Time to treatment failure (TTF)**

Time to treatment failure (TTF): It is defined as the time from the date of first administration to the date of treatment termination or death.

Censoring rules are as follows:

- If the treatment is unterminated, the censoring date will be the date of the last survival.

### **4.2. Safety Endpoints**

#### **4.2.1. Adverse events**

Treatment-emergent adverse events (TEAEs) are defined as any adverse events (AEs) that are new or worse than those at baseline (before treatment) after initiation of the study drugs.

#### **4.2.2. Laboratory test**

The laboratory test data of hematology, blood biochemistry, urinalysis, routine stool test, coagulation function test, thyroid function test, pituitary adrenal axis examination, viral examination, alpha fetoprotein, and pregnancy test will be collected at protocol-specified visit time points.

#### **4.2.3. Vital signs**

Vital signs including body temperature, pulse, breath, systolic blood pressure, and diastolic blood pressure will be collected at protocol-preset time points.

#### **4.2.4. Electrocardiogram (ECG)**

The data of heart rate, PR, QT, QTc, and QRS will be collected at protocol-preset time points.

#### **4.2.5. Physical examination**

Physical examination includes general condition, head and face, skin, lymph nodes, eyes, ears, nose, throat, mouth, respiratory system, cardiovascular system, abdomen (including liver and spleen), reproductive-urinary system, musculoskeletal system, nervous system, mental condition, and others. These data will be collected at protocol-specified visit/time points.

#### **4.2.6. Other safety endpoints**

Ultrasound cardiogram, ECOG PS, and other examinations.

### **4.3. Exploratory Endpoints**

#### **4.3.1. Pharmacokinetics and pharmacodynamics**

Not applicable.

#### **4.3.2. Immunogenicity**

Not applicable.

#### **4.3.3. Quality of life index**

Not applicable.

#### **4.3.4. Biomarker**

To explore the relationship between baseline alpha fetoprotein level and efficacy.

To explore the relationship between PD-L1 expression level in tumor tissue and efficacy.

#### **4.3.5. Other exploratory endpoints**

To explore the HBsAg loss during the trial.

## **5. STATISTICAL ANALYSIS**

### **5.1. General Considerations**

#### **5.1.1. Analysis sets**

##### **5.1.1.1. Full analysis set (FAS)**

The analysis set is based on the intention-to-treat principle. All enrolled subjects who have at least one medication record are included in this analysis set. The full analysis set is the primary analysis set for the efficacy analysis of this study.

##### **5.1.1.2. Safety analysis set (SS)**

All enrolled subjects who have received the study drugs at least once are included in the safety analysis set. This dataset is used for safety analysis.

##### **5.1.1.3. Evaluable analysis set (ES)**

All enrolled subjects who have received at least one study dose and at least one effective post-baseline imaging evaluation are included in this analysis set.

##### **5.1.1.4. PD-L1 analysis set (PD-L1)**

All enrolled subjects who have at least one medication record and have tumor biopsy samples for PD-L1 expression level detection are included in this analysis set.

### **5.1.2. General rule and analysis**

#### **Baseline**

Unless otherwise stated, the "baseline" in this study is defined as the last non-missing measurement value obtained prior to the first use of the study drugs, including the measurements taken on the day of and prior to the first dose.

#### **Study day**

The date of first administration is defined as the starting date of the study (Day 1) and the starting date of the study as the basis. The study days corresponding to the examination or event are calculated according to the following formula:

- If the examination/event date is prior to the starting date of the study, the study days = the examination date - the starting date of the study;
- If the examination/event date is on or after the starting date of the study, the study days = the examination date - the starting date of the study + 1.

## **General analysis**

Unless otherwise specified, the following descriptive statistical summary will be given according to variable type:

- The continuous variables are summarized by using mean, standard deviation, median, maximum, minimum, and quartile.
- The categorical variables are summarized by frequency and percentage.
- The time-to-event data: Kaplan-Meier method is used to estimate the survival function and the median time to event occurrence, and the survival curve is drawn.

## **Number of decimal places**

Unless otherwise specified, number of decimal places in the analysis report will be determined as per the following rules:

- The decimal places of the minimum and maximum will remain the same as those of raw data to be acquired; there should be one additional decimal place for the mean and median, and 2 additional decimal places for standard deviation, up to 4 decimal places.
- The percentage will be rounded to 1 decimal place. If the frequency is 0, the percentage is not displayed.
- The *P* value will retain four decimal places. If the *P* value is  $< 0.0001$ , it will be expressed as " $< 0.0001$ ". If the *P* value is  $> 0.9999$ , it will be reported as " $> 0.9999$ ".
- If there is a decimal in 95% CI, at least 2 decimal places and at most 4 will be retained. Details are as follows: The 95% CI has one more decimal place than that of the raw data. If the raw data have no decimal place, the 95% CI will retain 2 decimal places; if the raw data have 4 or more decimal places, the 95% CI will retain at most 4 decimal places.
- For time to event occurrence (month), one decimal place will be retained.

## **Analysis software**

All statistical analyses will be performed on the statistical analysis software SAS® v9.4.

## **Results of laboratory tests**

The results of laboratory tests are generally continuous numerical variables or character variables. If continuous numerical variables recorded in eCRF contain special characters (such as  $< xx$  and  $> xx$ ), the following rules will be applied:

- (1) When  $< xx$  or  $\leq xx$  appears, half value of  $xx$  will be taken for analysis.
- (2) When  $> xx$  or  $\geq xx$  appears, the value of  $xx$  will be taken for analysis.

### **5.1.3. Derived variables**

Refer to Section 5.5.1 "Extent of exposure" for the derived variables related to study drug exposure information, and for other derived variables, refer to the corresponding definition of derived rules in each section for details.

### **5.1.4. Covariates and subgroups**

Subgroup variables involved in the statistical analysis of this trial:

Age, gender, baseline ECOG PS, extrahepatic metastasis, vascular invasion, BCLC stage, body weight, HBV infection, baseline alpha fetoprotein level, etc. See Section 5.4.4 "Subgroup analysis" for details.

### **5.1.5. Analysis window**

For analysis that needs to be summarized according to the visits (visits after baseline, see Section 5.1.2 for the definition of baseline), it will be summarized based on the protocol visits filled in eCRF without considering whether the examination has exceeded the protocol-specified visit time window.

When safety analysis is conducted according to the visit, statistical analysis will be performed based on the planned protocol visit time points, that is, there is no need to present the unplanned protocol time points.

### **5.1.6. Missing data**

If the missing date and month needs to be imputed, they will be imputed in accordance with the Hengrui imputation rules for date-type data. The following imputation rules apply only to the missing data for AE occurrence date, first tumor pathology diagnosis date, system treatment history starting date, new anti-cancer treatment starting date, and death date. Other missing dates such as those for laboratory test, electrocardiogram examination, and vital signs will not be imputed.

#### **5.1.6.1. Adverse events**

If the date related to an AE is missing, the rules for imputing the date are as follows:

- If the starting date of an AE is completely missing, the date will be imputed with the date of the first administration.

- If only the day of the starting date of the AE is missing with the same year and month as those of the first administration, the day will be imputed with that of the date of the first administration.
- If both the month and day of the starting date of the AE are missing with the same year as that of the first administration, the month and day will be imputed with those of the date of the first administration.
- In other cases, if the month or day of the starting date of the AE is missing, it will be imputed with 1.
- If only the day of the ending date of the AE is missing, the date will be imputed with the last day of the month (before the date of death). If the last day of the month is later than the date of death, the date will be imputed with the date of death.
- In other cases, if the ending date of the AE is missing, the date will not be imputed.

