8. REPORTING OF ADVERSE EVENTS

8.1. Adverse Events (AEs)

8.1.1. Definition of AEs

An AE is any adverse medical occurrence in a study subject, which does not necessarily have a causal relationship with the trial intervention. Adverse events will be collected from the signing of the informed consent form until at least 30 days after the last dose. SAEs and irAEs observed within 90 days after the last dose of SHR-1210 should be followed up and collected. If the subjects start a new anti-tumor treatment, they should be followed-up until they start the tumor treatment (if the tumor treatment is started within 30 days after the last dose, the subjects should be followed-up until at least 30 days after the last dose; if the tumor treatment is started more than 30 days after the last dose, the subjects should be followed-up until they start the new tumor treatment). AEs can include any unfavorable and unexpected symptoms, signs, laboratory abnormalities or diseases, etc., including the following:

- 1) Worsening of pre-existing (prior to enrollment) medical conditions/diseases (including symptoms, signs, and laboratory abnormalities);
- 2) Any new AE: Any new adverse medical conditions (including symptoms, signs, and newly diagnosed diseases);
- 3) Abnormal clinically significant laboratory values or results that are not caused by concomitant diseases.

Any AEs should be recorded in details, including: the name of the AE and description of all relevant symptoms, onset time, severity, causes, correlation with the investigational drug, duration, measures taken, and final results and outcomes.

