#### 5.1.6.4. Starting date of new anti-cancer treatment

If the starting date of new anti-cancer treatment is incomplete, the rules for imputing the date are as follows:

- If the ending date of new anti-cancer treatment is partially missing or not missing, the ending date will be used to derive the starting date of new anti-cancer treatment:
  - If only month and day of the ending date of new anti-cancer treatment are missing but the year is not missing, the month and day will be imputed with 31 Dec. as the ending date of new anti-cancer treatment.
  - If only day of the ending date of new anti-cancer treatment is missing but the year and month are not missing, the day will be imputed with the last day of the month as the ending date of new anti-cancer treatment.
- If the starting date of new anti-cancer treatment is completely or partially missing, the rules for deriving and imputing the date are as follows:

○ The starting date of new anti-cancer treatment is completely missing

The starting date imputed = min [max (first PD date + 1, the date of last administration + 1), the ending date of new anti-cancer treatment]

○ Only the year (YYYY) of the starting date of new anti-cancer treatment is not missing

- 1) If YYYY < min (year) [max (first PD date + 1, the date of last administration + 1), the ending date of new anti-cancer treatment], the starting date will be imputed with 31 Dec., YYYY;
- 2) If YYYY = min (year) [max (first PD date + 1, the date of last administration + 1), the ending date of new anti-cancer treatment], the starting date will be imputed with min [max (first PD date + 1, the date of last administration + 1), the ending date of new anti-cancer treatment];
- 3) If YYYY > min (year) [max (first PD date + 1, the date of last administration + 1), the ending date of new anti-cancer treatment], the starting date will be imputed with 1 Jan., YYYY.

○ The year (YYYY) and month (MM) of the starting date of new anti-cancer treatment are not missing

- 1) If YYYY = min (year) [max (first PD date + 1, the date of last administration + 1), the ending date of new anti-cancer treatment] and MM < min (month) [max (first PD date + 1, the date of last administration + 1), the ending date of new anti-cancer treatment], the starting date will be imputed with the last day of MM-MM-YYYY;

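### Three AE start-date imputation rules move the start to the first dose without checking the end date, so an AE recorded as ended before treatment gets a start after its end

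*SAP*

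**What the plan says.** SAP 5.1.6.1 has four rules for an incomplete AE start date. Three of them lead to the first-dose date:

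- Start completely missing: "If the starting date of an AE is completely missing, the date will be imputed with the date of the first administration".
- Day missing: "If only the day of the starting date of the AE is missing with the same year and month as those of the first administration", then "the day will be imputed with that of the date of the first administration".
- Month and day missing, with the start in the first-dose year: "the month and day will be imputed with those of the date of the first administration".

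The fourth covers everything else: "In other cases, if the month or day of the starting date of the AE is missing, it will be imputed with 1".

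None of the four mentions the AE end date. The end-date rules in the same section fill a missing day with the last day of the month, cap the result at death, and leave less complete end dates alone. They do not refer to the start.

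Pre-dose events are in the data by design. Protocol 8.1.1 states: "Adverse events will be collected from the signing of the informed consent form until at least 30 days after the last dose". Protocol 6.1 allows screening up to 21 days before the first dose, and Protocol 7.2.1 has signs and symptoms at screening entered in the eCRF.

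SAP 4.2.1 and 5.5.2 define a TEAE as an event that is "new or worse than those at baseline (before treatment) after initiation of the study drugs". Under 5.5.2 only TEAEs are tabulated, all AEs are listed, and an AE with missing causality counts as drug-related.

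For new anti-cancer treatment the same SAP does use the other end of the interval. In 5.1.6.4, "the ending date will be used to derive the starting date of new anti-cancer treatment", and the imputed start is capped at that end date.

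**The concern.** Moving an unknown start to the first dose is a sensible conservative convention when the event might have begun on treatment. It has no purpose when the recorded end shows that the event was over before any drug was given. In that case the written rule produces an impossible sequence, with the start after the end. If the imputed start then decides TEAE status, a screening event enters the safety tables as a Cycle 1 treatment-emergent event.

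Two further effects are possible under extra conditions. If the term is one of the selected drug-related terms, the event enters the time-to-onset summary at day 1. If causality is missing, it is also counted as an ADR.

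**Working it through.** The plan gives no figure to reproduce. The check applies the printed rules to events that ended before the first dose.

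**One event.** First dose 20 April 2018; AE ended 12 April 2018.

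| Recorded start | Imputed start | On or after first dose? | Duration (end - start + 1) |
|---|---|---|---|
| missing | 20 April | yes | 12 - 20 + 1 = -7 days |
| April 2018 | 20 April | yes | -7 days |
| 2018 | 20 April | yes | -7 days |
| March 2018 | 1 March | no | 43 days |

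The first three rows start 8 days after the event ended. The formulas in SAP 5.5.2 then give cycle = integer part of (0 + 1)/28 + 1 = 1 and onset = (0 + 1)/7 = 0.14 weeks. The last row falls under the fourth rule and stays pre-treatment.

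**All pre-dose events.** Take every start-end pair lying wholly within day -21 to day -1, which is 21 × 22/2 = 231 pairs, for each first-dose date from 1 March to 31 December 2018 (306 dates). That gives 306 × 231 = 70,686 pairs. The date range follows the planned enrolment months. Equal weighting of pairs is an assumption.

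| Start recorded as | End known: dated on or after first dose | End known: start after end | End day missing: dated on or after first dose | End day missing: start after end |
|---|---|---|---|---|
| missing | 100% | 100% | 100% | 25% |
| year only | 100% | 100% | 100% | 25% |
| month and year | 53% | 53% | 53% | 0% |

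Hand check of the 53%. For a first dose on day d of a month, the pairs that start in that month number m(m + 1)/2, with m = min(21, d - 1). Summed over d = 1 to 21 this is 20 × 21 × 22/6 = 1,540, and 1,540/231 = 6.67 day-equivalents per month. Later days of the month count in full. Over 10 months: (10 × 6.67 + 306 - 210)/306 = 162.67/306 = 0.53.

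Hand check of the 25%. These are pairs whose end month precedes the first-dose month. Per month there are 21 × 22 × 23/6 = 1,771 pairs, and 1,771/231 = 7.67. Then 10 × 7.67/306 = 0.25.

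**With the start capped at a known end date.** 0 of 70,686 pairs are dated on or after the first dose and 0 start after their end, in all three patterns.

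**Sensitivity per event.** The planned population with first-line treatment failure is up to 120, and with the other 56 the total is 176. One extra subject adds 1/120 = 0.83 points or 1/176 = 0.57 points to a preferred term. The 5% reporting line is 6 of 120, or 9 of 176 (0.05 × 176 = 8.8). These figures hold for any single miscounted subject. They do not estimate the effect of this rule.

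**The case against.** The strongest reply is that SAP 5.1.6.1 assigns dates only. TEAE is defined by substance, and an event that ended before treatment fails that definition whatever start is imputed. A reader might infer that the SAP itself turns such events into TEAEs, or that TEAE rates will be wrong. The documents do not support that, because no date algorithm for TEAE status is written. What stands is narrower: the impossible date follows directly from the rule, and the misclassification follows if status is derived from the imputed start, which is the usual reason for having such a rule.

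Other points on that side:

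- SAP 5.1.6 refers to a company standard for date imputation that is not supplied. It may contain an end-date check. The AE rules printed in the SAP do not, so any check should be stated there.
- Protocol 8.1.1 asks for onset time for each AE, 12.1.2 wants no blank eCRF items, and 12.3.2 and 12.3.3 provide for queries and a review of missing values before lock. These controls make affected records rare. They do not correct the rule for records that remain.
- A reader might take all partial starts to be affected. The fourth rule excludes the rest, and among day-missing starts only those in the first-dose month move.
- The onset and ADR effects are not automatic. The selected-term lists are of drug-related events, so an event that ended before dosing would normally enter only if it was judged related or its causality was missing.
- The rule in 5.1.6.4 serves efficacy censoring, so it is an analogy and not a contradiction. It shows only that the SAP makes this kind of check elsewhere.

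**Conclusion.** Wrong as written, minor. For an AE with a recorded end before the first dose, the first three start-date rules in SAP 5.1.6.1 give a start after the end whenever they apply and the end date is complete. Counting the event as treatment-emergent rests on the assumption that TEAE status is taken from the imputed start.

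The number of affected events is not in the documents and is probably small, so the effect on TEAE rates cannot be sized. The effect is confined to safety tables and does not touch the primary endpoint. The convention itself is sound when the end is unknown or on or after the first dose. Only the missing end-date condition is at fault.

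**What to change.** Amend SAP 5.1.6.1 along these lines:

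> The first three start-date rules apply only if the AE end date is missing, or if its recorded parts allow an end on or after the first dose. If the complete or partial end date shows that the event ended before the first dose, the start is set to the earlier of the AE end date (after end-date imputation) and the day before the first dose, and the event is not treatment-emergent.

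The SAP imputes an end date only when the day alone is missing. If the end is known only to a year before the first-dose year, take 31 December of that year as the end for this step. Otherwise the start could fall after the recorded end year.

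The conservative handling of uncertain cases is kept. An end known only to the first-dose month still leaves the event imputed to the first dose.

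The cost is a short SAP edit and a few lines of code, with no new data. There is one small downside: a wrongly recorded end date could remove an event from the TEAE tables. Such records should be queried before database lock, and they remain in the listing of all AEs.

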#### **5.1.6.2. Medical history**

If the date of past medical history (that is before first administration of the study drugs including first tumor pathological diagnosis date and others) is missing, the rules for imputing the date are as follows:

- If the day is missing, the day will be imputed with 1 of the month.
- If both month and day are missing and the year is prior to the year of the first administration, the date will be imputed with 1 Jan.
- If both month and day are missing and the year is the same as that of the first administration, the date will be imputed with 1 Jan.
- If the date is completely missing, it will not be imputed.

#### **5.1.6.3. Starting date of systemic treatment history**

If the starting date of systemic treatment history is missing, the rules for imputing the date are as follows:

- If the day is missing, the day will be imputed with 1 of the month.
- If both month and day are missing and the year is prior to the year of the first administration, the date will be imputed with 1 Jan.
- If both month and day are missing and the year is the same as that of the first administration, the date will be imputed with 1 Jan.
- If the date is completely missing, it will not be imputed.

#### 5.1.6.4. Starting date of new anti-cancer treatment

If the starting date of new anti-cancer treatment is incomplete, the rules for imputing the date are as follows:

- If the ending date of new anti-cancer treatment is partially missing or not missing, the ending date will be used to derive the starting date of new anti-cancer treatment:
  - If only month and day of the ending date of new anti-cancer treatment are missing but the year is not missing, the month and day will be imputed with 31 Dec. as the ending date of new anti-cancer treatment.
  - If only day of the ending date of new anti-cancer treatment is missing but the year and month are not missing, the day will be imputed with the last day of the month as the ending date of new anti-cancer treatment.
- If the starting date of new anti-cancer treatment is completely or partially missing, the rules for deriving and imputing the date are as follows:

○ The starting date of new anti-cancer treatment is completely missing

The starting date imputed = min [max (first PD date + 1, the date of last administration + 1), the ending date of new anti-cancer treatment]

○ Only the year (YYYY) of the starting date of new anti-cancer treatment is not missing

- 1) If YYYY < min (year) [max (first PD date + 1, the date of last administration + 1), the ending date of new anti-cancer treatment], the starting date will be imputed with 31 Dec., YYYY;
- 2) If YYYY = min (year) [max (first PD date + 1, the date of last administration + 1), the ending date of new anti-cancer treatment], the starting date will be imputed with min [max (first PD date + 1, the date of last administration + 1), the ending date of new anti-cancer treatment];
- 3) If YYYY > min (year) [max (first PD date + 1, the date of last administration + 1), the ending date of new anti-cancer treatment], the starting date will be imputed with 1 Jan., YYYY.

○ The year (YYYY) and month (MM) of the starting date of new anti-cancer treatment are not missing

- 1) If YYYY = min (year) [max (first PD date + 1, the date of last administration + 1), the ending date of new anti-cancer treatment] and MM < min (month) [max (first PD date + 1, the date of last administration + 1), the ending date of new anti-cancer treatment], the starting date will be imputed with the last day of MM-MM-YYYY;
- 2) If YYYY = min (year) [max (first PD date + 1, the date of last administration + 1), the ending date of new anti-cancer treatment] and MM = min (month) [max (first PD date + 1, the date of last administration + 1), the ending date of new anti-cancer treatment], the starting date will be imputed with min [max (first PD date + 1, the date of last administration + 1), the ending date of new anti-cancer treatment];
- 3) If YYYY = min (year) [max (first PD date + 1, the date of last administration + 1), the ending date of new anti-cancer treatment] and MM > min (month) [max (first PD date + 1, the date of last administration + 1), the ending date of new anti-cancer treatment], the starting date will be imputed with 01-MM-YYYY;
- 4) If YYYY < min (year) [max (first PD date + 1, the date of last administration + 1), the ending date of new anti-cancer treatment], the starting date will be imputed with the last day of MM-MM-YYYY;
- 5) If YYYY > min (year) [max (first PD date + 1, the date of last administration + 1), the ending date of new anti-cancer treatment], the starting date will be imputed with 01-MM-YYYY.

